6.2 INTERIM ANALYSES AND FINAL ANALYSES

Interim analyses will be conducted after all subjects have been assessed for 3, 6, and 12 months. Although the results will be unblinded, per-subject randomization will not be disclosed to subjects, site personnel and the sponsor's clinical research staff to maintain the blind at the subject-level for the duration of the study. The study will not be stopped for claims of efficacy at these analyses. However, the study may be stopped for futility or safety at any time. No adjustments for the interim analyses will be conducted.

6.3 ADJUSTMENT FOR MULTIPLE COMPARISONS

No adjustments for multiple comparisons will be made in this study.

6.4 EXTENT OF EXPOSURE

The duration of exposure will be calculated for each subject. Summary statistics will be presented for each treatment group using the Intent-to-Treat population.

This Document is Company Confidential Page 9 of 13

6.5 SUBJECT DISPOSITION

Subject disposition will be summarized in terms of the number of subjects who completed the study and discontinued early from the study. Disposition will be summarized for each treatment group using the Intent-to-Treat population.

6.6 **DEVIATIONS**

The total number of each deviation type will be summarized for the Intent-to-Treat population.

6.7 DEMOGRAPHIC AND BASELINE CHARACTERISTICS

Demographic and baseline characteristics, consisting of previous testosterone therapy use, hypogonadal symptom history, disease history (diabetes, hypertension, hypercholesterolemia, depression, erectile dysfunction, hypothyroidism, and sleep apnea), age, and race will be summarized.

Demographics will be summarized for the Intent-to-Treat population. Demographic and baseline data will be listed for all subjects to supplement summary results. Results will be presented for each treatment group.

6.8 EFFICACY ANALYSES

Efficacy analyses will be conducted using the Intent-to-Treat population, as defined in Section 4.1.

6.8.1 Lean Body Mass

Lean body mass, bone mass, body fat mass, and percentage of total for each will be determined by DXA at baseline and over time. Pairwise comparisons between treatment groups will be performed using t-tests and Wilcoxon rank-sum tests, as appropriate. Within each treatment group the statistical significance of the change/percentage change from baseline will be based on a paired t-test or Wilcoxon signed-rank test, as appropriate.

For measures obtained by DXA, baseline will be defined as the earliest assessment, regardless of relation to the start of study medication.

6.8.2 Body Strength

Gains in strength over time will be assessed by changes/percentage changes in maximum single repetition chest/leg press. Pairwise comparisons between treatment groups will be performed using t-tests and Wilcoxon rank-sum tests, as appropriate. Within each treatment group the statistical significance of the change/percentage change from baseline will be based on a paired t-test or Wilcoxon signed-rank test, as appropriate.

For body strength measures, baseline will be defined as the earliest assessment, regardless of relation to the start of study medication.

6.8.4 Testosterone, LH, DH1, E2, DH1:Testosterone, Testosterone:E2

Testosterone, LH, DHT, E2, DHT:testosterone, and testosterone:E2 levels will be measured at baseline and over time. Pairwise comparisons between treatment groups will be performed using t-tests and Wilcoxon rank-sum tests, as appropriate. Within each treatment group the statistical significance of the change/percentage change from baseline will be based on a paired t-test or Wilcoxon signed-rank test, as appropriate.

Two separate baselines will be defined for testosterone, a true baseline record as defined in Section 6.1, and a screening baseline, defined as the average of all screening testosterone measurements. A separate 'change from baseline' will be calculated using each.

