8. TRIAL DESIGN

8.1 Study Design

8.1.1 Overview of Study Design

Protocol ZA-205 is a randomized, double-blind, placebo-controlled multi-center study to compare changes in weight, lean body mass (using DXA), waist circumference, glycemic parameters and scores using various subject questionnaires following treatment with 12.5 or 25 mg enclomiphene or placebo in overweight men with acquired hypogonadotropic hypogonadism and waist circumference ≥ 40 inches (101.6 cm). The study requires 7 clinic visits and is approximately 15 months in duration. Subjects will be provided with a 15 month gym membership and personal trainer, and will exercise for 30-45 minutes three times a week. They will also receive a 6 month commercial diet program. Subjects will be treated for 12 months. [REDACTED]

The study will enroll 45 male subjects, 15 randomized to treatment with enclomiphene 12.5 mg, 15 randomized to enclomiphene 25 mg and 15 randomized to placebo, in a 1:1:1 ratio.

Eligible subjects must have 2 consecutive assessments of morning T at Visit 1 (screening). The assessments must be 2-4 days apart and both must be 300 ng/dL or less. Subjects must also have LH >1.4 and < 9.4 mIU/mL at Screening. Waist circumference must be ≥ 40 inches (101.6 cm). Subjects must not have been treated with testosterone products in the 6 months prior to the study. They must not have used testosterone products for 12 months or longer at any time in the past. Subjects will follow a commercial diet plan and exercise with a personal trainer at least 3 times a week. At clinic visits, clinical laboratory assessments will be performed and subject questionnaires will be administered. Subjects will be called every 2 weeks to check on compliance with their exercise regimen and diet, and solicit adverse events. [REDACTED]

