8.2.1 Inclusion Criteria

Subjects must meet the following criteria:

[figure not shown]
1. Overweight (BMI 30 to 42 kg/m² inclusive) males age 18 to 60 inclusive
2. Waist circumference \geq 40 inches (101.6 cm)
3. Previously or concurrently diagnosed as having secondary hypogonadism.
4. Must have 2 morning testosterone assessments at Visit 1, collected before 10 AM, 2-4 days apart, and both of which must be \leq 300ng/dL.
5. LH >1.4 and <9.4 mIU/mL (at Visit 1 only)
6. HbA1c ≤ 7.5
7. Stable weight for last 3 months (+/- 10 pounds)
8. Lives or works within 10 miles of the gym that will be used for the study
9. Must be fit enough to participate in the fitness program
10. Ability to complete the study in compliance with the protocol requirements
11. Ability to understand and provide written informed consent

[figure not shown]

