3. STUDY DESIGN

3.1 OVERVIEW AND LENGTH OF STUDY

Protocol ZA-205 is a randomized, double-blind, placebo-controlled multi-center study to compare changes in metabolic parameters following treatment with 12.5 mg or 25 mg of enclomiphene or placebo in conjunction with a 6-month diet and 15 month exercise program, in overweight men with acquired hypogonadotropic hypogonadism. Subjects will receive a 15-month gym membership with personal trainer for 12 months, a Fitbit and a 6 month commercial diet program. The study requires 7 clinic visits and is approximately 15 months in duration. Subjects will be treated with enclomiphene or placebo for 12 months.

A schedule of procedures and assessments is displayed in Section 4 of the ZA-205 protocol. The study will enroll 45 male subjects, 15 randomized to treatment with enclomiphene 12.5 mg, 15 randomized to treatment with 25 mg enclomiphene, and 15 randomized to Placebo, in a 1:1:1 ratio.

Eligible subjects must have 2 consecutive screening assessments of morning testosterone ≤ 300 ng/dL; however testosterone measured at the baseline visit may be > 300 ng/dL. LH must be > 1.4 mIU/mL and below 9.4 mIU/mL at screening. Waist circumference must be ≥ 40 inches (101.6 cm).

In addition to a central lab used for blood analyses, a second lab using LCMS will analyze testosterone, estradiol, free testosterone, and dihydrotestosterone. The results from each lab will be treated as separate analytes.

This Document is Company Confidential Page 7 of 13

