6. STATISTICAL METHODOLOGY AND ANALYSES

6.1 GENERAL CONSIDERATIONS

Standard statistical methods will be employed to analyze all data. The following techniques may be used: paired t-test; independent two-sample t-test; ANOVA; chi-square test; and Fisher's exact test. Assumptions of normality will be tested using the Shapiro-Wilk test. If distributional assumptions are violated, non-parametric techniques, such as the Wilcoxon signed-rank test, Wilcoxon rank-sum test, and Kruskal-Wallis test, will be employed. Summaries for quantitative variables will include the sample size, mean, median, standard deviation, minimum, and maximum. Summaries for categorical variables will include the number and percent of patients for each outcome. All summaries will be prepared for each dose level and treatment group, resulting in 4 analysis groups: 12.5 mg enclomiphene, 25 mg enclomiphene, pooled 12.5 and 25 mg enclomiphene, placebo.

Baseline will be defined as the most recent assessment that occurs on or before the start of study medication, unless otherwise specified.

Statistical significance will be declared if the two-sided p-value is ≤ 0.05 .

Additional statistical analyses, other than those described in this SAP, may be performed if deemed appropriate.

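### SAP 6.8.4 tests within-arm testosterone change from a baseline built on the values used to select men at 300 ng/dL or less, so that test rejects too often when nothing has changed; the comparisons with placebo are unaffected.

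*SAP*

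**What the plan says.** Selection. Protocol 8.2.1, criterion 4, reads "Must have 2 morning testosterone assessments at Visit 1, collected before 10 AM, 2-4 days apart", with a ceiling of 300 ng/dL on each. Protocol 8.1.1 repeats the rule: "The assessments must be 2-4 days apart and both must be 300 ng/dL or less".

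Baselines. SAP 6.1 sets the general rule: "Baseline will be defined as the most recent assessment that occurs on or before the start of study medication". For testosterone, SAP 6.8.4 keeps that record and labels it the true baseline, then adds a second: "a screening baseline, defined as the average of all screening testosterone measurements". On their use it says: "A separate 'change from baseline' will be calculated using each". No precedence between the two is stated.

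Tests. SAP 6.8.4 plans pairwise comparisons between groups, and also: "Within each treatment group the statistical significance of the change/percentage change from baseline will be based on a paired t-test or Wilcoxon signed-rank test". SAP 6.1 declares significance at a two-sided p-value of 0.05 or less and adds a pooled enclomiphene group. SAP 6.3 makes no multiplicity adjustment.

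The baseline visit. SAP 3.1 says eligibility does not depend on that draw: "however testosterone measured at the baseline visit may be" above 300 ng/dL. Only the screening values are truncated.

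The issue of 29 July 2016 is cited here. The issue of 3 May 2016 has the same wording in 6.8.4.

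**The concern.** Each screening value is a man's usual level plus that day's error, biological and analytical. Requiring both values to be at or below a cut-off favours men whose errors were negative on those days. Averaging the two draws shrinks the effect but does not remove it, because both had to pass. The screening average of the enrolled men therefore lies below their usual level, and a later draw is higher in expectation even if nothing has happened.

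A paired or signed-rank test of change from that average takes zero as its null value, although the expected change under no effect is above zero. Three consequences follow. Any arm can be reported with a significant testosterone rise that is partly or wholly an artefact. In the placebo arm, where every man also starts a diet and exercise programme, such a rise could be read as a lifestyle effect. And since the SAP computes change from two baselines without ranking them, one arm at one visit can yield two conflicting within-arm verdicts.

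**Working it through.** **Inputs from the documents.** Both screening draws at or below 300 ng/dL (Protocol 8.1.1, 8.2.1); baseline = mean of the screening draws (SAP 6.8.4); 15 men per arm (SAP 3.1), so 15 + 15 = 30 in the pooled group (SAP 6.1); two-sided 0.05 (SAP 6.1). No testosterone mean, SD or power figure is given, so there is no planned figure to reproduce.

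**Direction.** Write a man's usual level as t, the screening errors as e1 and e2, and the follow-up error as e4. With no true change,

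change = (t + e4) − [t + (e1 + e2)/2] = e4 − (e1 + e2)/2.

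If e4 is independent of selection its mean is zero, so the expected change is −E[(e1 + e2)/2 | t + e1 ≤ 300 and t + e2 ≤ 300]. Selection makes that conditional mean negative, so the expected change is positive. This needs no SD; only the size does.

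**Size (simulation, zero treatment effect, paired t-test, absolute change).** All means and SDs below are assumptions. Model A uses within-man error proportional to the level (CV). Model B uses additive error with a fixed within-man SD.

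| Model | Screened mean | Between-man SD | Within-man | Apparent rise (ng/dL) | Rejection, n = 15 | Rejection, n = 30 |
|---|---|---|---|---|---|---|
| A | 225–250 | 75–100 | CV 10–20% | +2 to +10 | 5.5–9% | – |
| A | 275 | 100 | CV 10% | +3 | 6% | – |
| A (middle) | 325 | 75 | CV 15% | +13 | 16% | 31–32% |
| A (extreme) | 375 | 75 | CV 20% | +35 | 43% | 78% |
| B | 250 | 80 | SD 30 | +2.8 | 5.6% | 7.0% |
| B | 300 | 80 | SD 60 | +19.0 | 16.2% | 29.3% |
| B | 350 | 80 | SD 75 | +39.8 | 36.9% | 67.0% |

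The signed-rank test does not escape: in model A it rejects in about 14% of arms in the middle case and 41% in the extreme case.

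**Hand check of the model B middle row.**
- Mean shift: the enrolled men average 214 ng/dL at screening and 233 at the baseline visit; 233 − 214 = 19.
- SD of the change, ignoring the trimming by selection: 60 × √(1 + 1/2) = 73.5.
- n = 15: standard error 73.5/√15 = 19.0, so the shift is 19.0/19.0 = 1.00 standard errors. By the normal approximation, rejection ≈ Φ(−0.96) + Φ(−2.96) ≈ 0.17 (simulated 0.162).
- n = 30: standard error 73.5/√30 = 13.4, so the shift is 19.0/13.4 = 1.42. Rejection ≈ Φ(−0.54) + Φ(−3.38) ≈ 0.29 (simulated 0.293).

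**Controls.** In model B, change from a separate baseline-visit draw with independent error has a mean of about 0, and the within-arm test rejects in 4.8% to 5.2% of arms. The between-arm test on the screening baseline rejects in 4.7% to 5.3%: randomisation gives every arm the same expected shift, and it cancels.

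**If errors carry over between visits.** Take the model A middle case with correlation 0.5 between errors at successive draws. Change from the baseline visit is then about +5 ng/dL with 7% rejection if the follow-up error is also correlated with the preceding draw. It is about +10 ng/dL with 9% if the follow-up error is independent; in that second setting the screening baseline rejects in 25%.

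**The case against.** The strongest reply is that little depends on this test. Protocol 7 lists testosterone under additional objectives, as a difference from placebo, and the endpoint in SAP 5 compares enclomiphene with placebo. The study is hypothesis-generating, and the SAP already reports change from the unselected record beside the other. Since all arms begin diet and exercise together, within-arm change does not isolate a drug effect on either baseline. This stands as a limit on consequence. It does not centre the test, and the SAP neither ranks the baselines nor marks one as descriptive.

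The size can also be disputed. The 43% needs a screened mean of 375 ng/dL with the largest within-man variation considered. Candidates must carry a diagnosis of secondary hypogonadism, so a mean below the cut-off is at least as plausible, and at 225 to 250 the inflation is small. That also stands.

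SAP 3.1 treats results from the central laboratory and the second (LCMS) laboratory as separate analytes, and the documents do not say which decides eligibility. In the assay not used for selection, the artefact would keep its biological part but lose the analytical part. The table does not separate the two.

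A reader might take SAP 3.1 as admitting regression to the mean. It only says the baseline-visit value may exceed 300 ng/dL and does not say why.

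A reader might also want men without a baseline-visit draw removed from the within-arm tests, because SAP 6.1 would then fall back on a screening value. The fallback is real, but nothing in the documents suggests such gaps will be common, and exclusion sits awkwardly with the intent-to-treat rule in SAP 4.1 and 6.8.

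**Conclusion.** The within-arm test of testosterone change from the screening baseline is biased upward. The direction follows from the entry rule. The size depends on assumed variability: from an inflation too small to matter, through +13 ng/dL and 16% rejection at n = 15 in the middle case, to +35 ng/dL and 43% at the extreme. The pooled group fares worse because the same shift is tested with a smaller standard error.

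Two stronger readings are not supported. One is that an ineffective treatment is bound to show a rise. The shift holds in expectation only: with a screened mean of 275 ng/dL, 18% to 34% of null arms of 15 show no rise. The other is that the trial's testosterone conclusions are compromised. Those are comparisons with placebo, and they stay at the nominal level on either baseline.

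The point is worth correcting because the rule as written raises the error rate of a planned test and the remedy is simple.

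**What to change.** In SAP 6.8.4:

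1. Use the pre-dose baseline-visit testosterone, the record the SAP labels the true baseline, for within-arm change and its tests.
2. Report within-arm change from the screening average descriptively, without p-values.
3. Use change from the screening average for inference only in comparisons of enclomiphene with placebo.

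No rule excluding men is needed. The baseline-visit value removes the bias fully only if its errors are independent of the screening errors; otherwise it reduces it, so a sentence to that effect should accompany the within-arm results.

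The cost is wording: no new data, no design change. One set of within-arm p-values is lost, and the reported within-arm rise may look slightly smaller.

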6.8.5 Metabolic Parameters

HbA1c, FPG, Insulin, HOMA-IR, C-reactive protein, Interleukin-6, TNF- α , leptin, and Quantos IR levels will be measured at baseline and over time. Pairwise comparisons between treatment groups will be performed using t-tests and Wilcoxon rank-sum tests, as appropriate. Within each treatment group the statistical significance of the change/percentage change from baseline will be based on a paired t-test or Wilcoxon signed-rank test, as appropriate.

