13.2.3 Efficacy Analyses

The analysis of each efficacy endpoint will be conducted in the intent-to-treat (ITT) population, defined as all subjects randomized to treatment with enclomiphene or placebo. The ITT population will be determined prior to unblinding the study data and reasons for any subjects excluded will be explained in the clinical study report. Handling of missing data will be described in the Statistical Analysis Plan (SAP) [REDACTED]

[REDACTED] t will be of interest to investigate various prognostic factors, such as age and diet compliance, to determine how these affect treatment response. Those factors will be noted in the SAP.

13.2.3.1 *Lean Body Mass*

Lean Body Mass (LBM) will be determined by DXA at baseline, 6 months and end of study. The change from baseline in lean body mass will be investigated with at least two measurements:

- Percentage change in LBM
- Change in LBM percentage (%LBM)

[figure not shown]
Subjects are expected to gain LBM and percentage LBM. Within and between treatment group t-tests or appropriate non-parametric methods will assess treatment affect. Descriptive statistics will summarize the results.

13.2.3.2 *Body Strength*

Strength will be assessed over the course of the study by assessments of the maximum Leg and Chest Press weight obtained. These values will be assessed at baseline and weekly. The baseline assessment will be determined at the subject's first gym visit. Analyses will compare the periodic assessments to the subject's baseline. Within and between treatment group t-tests or appropriate non-parametric methods will assess treatment affect. Descriptive statistics will summarize the results.

13.2.3.3 *Waist Circumference*

Careful assessments of waist circumference will detect change in body composition. The change in waist circumference over the duration of the study will be calculated and summarized using descriptive statistics. The change from baseline will be compared within and between treatment groups using a t-test or appropriate non-parametric method.

13.2.3.5 *Testosterone*

For each treatment group, the T and change from baseline in T (visit value minus baseline value) will be summarized at each treatment visit using descriptive statistics (sample size, mean, median, standard deviation, minimum and maximum). The change from baseline in T will be compared within and between treatment groups using a t-test or appropriate non-parametric method.

13.2.3.6 *LH*

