For each treatment group, the LH and change from baseline in LH (visit value minus baseline value) will be summarized at each treatment visit

using descriptive statistics (sample size, mean, median, standard deviation, minimum and maximum). The change from baseline in LH will be compared within and between treatment groups using a t-test or appropriate non-parametric method.

13.2.3.7 *Metabolic Parameters*

For each treatment group, the HbA1c, FPG, Insulin, HOMA-IR and Quantose IR assessment of insulin sensitivity and change from baseline will be summarized at each treatment visit using descriptive statistics (sample size, mean, median, standard deviation, minimum and maximum). The change from baseline will be compared within and between treatment groups using a t-test or appropriate non-parametric method.

13.2.3.8 *Change in BMI*

For each treatment group, the weight and change from baseline in BMI (visit value minus baseline value) will be summarized at Week 16 using descriptive statistics (sample size, mean, median, standard deviation, minimum and maximum). The change from baseline in BMI will be compared within and between treatment groups using a t-test or appropriate non-parametric method.

[REDACTED]

[REDACTED]

[REDACTED]

[REDACTED]

[REDACTED]

[REDACTED]

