5. ENDPOINTS

Efficacy endpoints include:

- Changes in lean body mass (LBM), assessed using DXA
- Changes in waist circumference, comparing enclomiphene to placebo
- Changes from baseline in testosterone, comparing enclomiphene to placebo
- Values and changes in values from baseline in luteinizing hormone (LH), hemoglobin A1c (HbA1c), fasting plasma glucose (FPG), high sensitivity C-reactive protein, Interleukin-6, tumor necrosis factor (TNF-α) receptor 2, and leptin, comparing enclomiphene to placebo
- Change in strength assessed from maximum chest and leg press weight achieved
- Changes in insulin resistance determined by homeostasis model of insulin resistance (HOMA-IR) and Quantose IR[™] (Metabolon Inc.), comparing enclomiphene to placebo
- Change in weight and BMI, comparing enclomiphene to placebo
- Values for dihydrotestosterone (DHT) and estradiol (E2), and the ratios of DHT:testosterone and testosterone:E2

This Document is Company Confidential Page 8 of 13

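### No visible between-group comparison adjusts for the baseline value: the planned tests are valid, but precision at 15 v 15 could be modestly better

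*SAP*

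**What the plan says.** SAP 6.8.1, 6.8.2, 6.8.4, 6.8.5 and 6.8.6 share one sentence on between-group tests: "Pairwise comparisons between treatment groups will be performed using t-tests and Wilcoxon rank-sum tests, as appropriate". It does not say whether the compared variable is the value, the change or the percentage change. Change is mentioned in the sentence that follows, which concerns within-group tests.

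The protocol supplies the variable. In 13.2.3, for example for the metabolic parameters, it says: "The change from baseline will be compared within and between treatment groups using a t-test or appropriate non-parametric method". For lean body mass it names two measures, "Percentage change in LBM" and the change in percentage lean mass.

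SAP 5 lists LH, HbA1c, FPG, hsCRP, IL-6, TNF receptor 2 and leptin both as values and as changes. One group appears as values only: "Values for dihydrotestosterone (DHT) and estradiol (E2), and the ratios of DHT:testosterone and testosterone:E2".

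The general menu in SAP 6.1 reads "The following techniques may be used: paired t-test; independent two-sample t-test; ANOVA", followed by chi-square, Fisher and rank tests. It contains no ANCOVA or regression. The same section also says: "Additional statistical analyses, other than those described in this SAP, may be performed if deemed appropriate".

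Protocol 13.2.3 expresses interest in "various prognostic factors, such as age and diet compliance, to determine how these affect treatment response. Those factors will be noted in the SAP". The visible SAP lists no such factors.

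**The concern.** Every endpoint has a baseline measurement, and in the visible text that measurement is at most subtracted from the follow-up value, or used as the divisor of a percentage. For endpoints listed as values only, it may not be used at all.

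Subtracting baseline is the efficient choice only when the regression slope of follow-up on baseline is near 1, and ignoring baseline is efficient only when the slope is near 0. Between these, both leave avoidable noise and part of any chance baseline imbalance in the estimate.

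The trial has 15 men per arm, no sample-size calculation and a hypothesis-generating aim, so its useful product is a set of effect estimates and their uncertainty. The visible text plans no confidence intervals. The intervals below are those implied by the t-tests, and the same loss would appear as lower power.

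**Working it through.** The plan states no power, effect size or SD, so there is no figure of its own to reproduce.

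**Inputs.** From the documents: 15 per arm (SAP 3.1), two-sided 0.05 (SAP 6.1), and a pooled active group (SAP 6.1), hence 30 v 15. Assumed: rho, the correlation of baseline with follow-up, and k, the follow-up SD divided by the baseline SD.

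**Variances**, in units of baseline variance:
- value: k²
- change: 1 + k² − 2·rho·k
- ANCOVA: k²(1 − rho²), multiplied at 15 v 15 by 1 + 1/(30 − 4) = 27/26 for chance baseline imbalance

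**Width ratio** = √(variance ratio) × t(27)/t(28), with t(27)/t(28) = 2.0518/2.0484.

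Example at k = 1, rho = 0.3: variance ratio to change = 0.91/1.40 × 27/26 = 0.675, so the width ratio is 0.82. Against the value: 0.91 × 27/26 = 0.945, so the width ratio is 0.97.

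**95% interval width at 15 v 15, ANCOVA / change score:**

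| k | rho 0.3 | rho 0.5 | rho 0.7 | rho 0.9 |
|---|---|---|---|---|
| 0.75 | 0.69 | 0.74 | 0.76 | 0.72 |
| 1 | 0.82 | 0.88 | 0.94 | 0.99 |
| 1.5 | 0.95 | 1.00 | 1.02 | 0.90 |
| 2 | 1.00 | 1.02 | 0.98 | 0.75 |

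**Against the better of value and change, k = 1.** The value has the smaller variance below rho 0.5 and the change above it, because 1 = 2(1 − rho) at rho = 0.5. At rho 0.3 the comparator is the value (ratio 0.97), at 0.5 the two tie (0.88), and at 0.7 it is the change (0.94). The gains are about 3%, 12% and 6%.

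**Validity.** In simulation at 15 v 15 with equal SDs, the type I error was 0.047 to 0.051 for the change-score t-test and 0.049 to 0.051 for ANCOVA. With SDs that differ between arms, the two-arm ANCOVA stayed between 0.048 and 0.054.

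**Imputation.** Protocol 13.3 imputes no change for a subject with no post-baseline efficacy data. If an assumed 20% of subjects are set to their baseline, k stays at 1 and rho becomes 0.8·rho + 0.2, that is 0.44, 0.60 and 0.76. At k = 1 the variance ratio to change is (1 + rho)/2 × 27/26, giving width ratios of 0.87, 0.91 and 0.96. The gain against change falls to about 13%, 9% and 4%.

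**Drop-out.** At an assumed 10 v 10, k = 1.5 and rho = 0.7, the widening is about 3%.

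**Pooled doses v placebo, 30 v 15.** At a common k = 1 the width ratios are 0.82, 0.88, 0.93 and 0.99 for rho 0.3, 0.5, 0.7 and 0.9. If the active SD ratio is 2 and placebo is 1 (assumed), the simulated variance ratios to change are 0.87, 0.98, 1.08 and 1.13, so adjustment can cost up to 13% in variance. With unequal SDs the common-variance ANCOVA also loses its nominal size: 0.019 to 0.037 with the active ratio at 1.5 or 2, and 0.073 to 0.078 with it at 0.75. A Welch test on change stays at 0.048 to 0.052.

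**Choice of scale.** Subtracting baseline from both sides of the ANCOVA alters only the baseline slope. The treatment estimate is the same whether the outcome is the value or the change.

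**The case against.** The strongest reply is that this is a preference about efficiency. The planned tests are valid, the analyses are described as mainly descriptive, and no decision rule hangs on interval width. That stands, and it sets the severity.

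The second reply is that an 18% gain arises only against the change score. For the seven analytes that SAP 5 lists on both scales, the plan also provides the value, and at k = 1 and rho 0.3 the gain over the value is about 3%. That stands too. What remains is that the plan gives no rule for which scale leads, and the better one cannot be known before rho and k are.

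Third, the figures before imputation assume complete data, and Protocol 13.3 reduces the gain as shown above.

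Fourth, parts of Protocol 13.2.3 and 13.3 are blacked out, SAP text is missing around 6.8.3 and after 6.8.6, and SAP 6.1 permits further analyses. A reader might infer that the trial has no baseline adjustment at all; the documents support only that none is visible. The permission in SAP 6.1 does not itself specify one, and an adjustment chosen after unblinding carries less weight than one written down beforehand. The prognostic-factor sentence concerns how factors affect response and names neither the baseline value nor a method.

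**Conclusion.** The point holds as a low-severity, optional improvement. In the visible text no between-group comparison uses the baseline value as a covariate. Under assumed k = 1 and rho of 0.3 to 0.7, and against the better of the two planned scales, adjusting would narrow 15 v 15 intervals by about 3 to 12%.

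The gain varies by endpoint. It is near nil for measures that track closely (rho near 0.9, k near 1), as lean mass or weight may. It is small or nil at k of 1.5 to 2 with rho of 0.3 to 0.7, as may apply to testosterone, where the entry limit can narrow baseline spread. The documents give rho and k for no variable. The width formula applies to the t-test, not the rank-sum test.

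Three stronger readings are tempting and not supported:
- That the planned comparisons are biased or invalid. Randomisation protects them, and the simulated error rates are nominal at 15 v 15.
- That baseline always enters as change. Four variables are listed as values only, and the SAP sentence names no variable.
- That 18% is the general gain. It is the k = 1, rho 0.3 result against the weaker of the two scales.

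**What to change.** In SAP 6.8.1 and 6.8.4 to 6.8.6, with matching wording in Protocol 13.2.3:

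- **Each dose v placebo:** specify an ANCOVA of the visit value (or change) on treatment plus that variable's pre-dose baseline. Fit it on the two arms compared, report a 95% confidence interval, and use the same imputation rule as the planned analysis. Keep the planned t-test or rank test as supporting.
- **Pooled doses v placebo:** keep the planned change comparison as the main one, in Welch form, with the ANCOVA as supporting.
- **DXA:** SAP 6.8.1 takes the earliest scan as baseline even if it follows the first dose. Use as covariate only a scan taken on or before the first dose. Where any subject lacks one, keep the planned comparison in all randomised subjects as main and report the adjusted result as a sensitivity analysis.
- **Strength (6.8.2):** leave as planned. Its baseline is also the earliest assessment whatever its timing, and Protocol 13.2.3.2 places it at the first gym visit.

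Which testosterone baseline leads, and which analytes are log-transformed, are separate questions and not part of this change.

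The cost is wording in two documents, minor programming and one degree of freedom. At 15 v 15 the interval could be up to about 2% wider in the settings examined, and slightly more with drop-out. No new data or procedures are needed.
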